Assessment of the prognostic value of nerve damage biomarkers in acute and chronic organophosphate toxicity

Study protocol

JULY 30, 2023

INTRODUCTION

Organophosphates are among the most easily accessible toxic compounds worldwide. The global occurrence of poisoning due to organophosphates is estimated to be 300,000 to 2 million cases per year, varying between accidental exposure and suicidal attempts ^(1,2). Owing to the high incidence of exposure, research focused on the detection of the possible mechanisms of toxicity, as well as evaluation of various antidote efficacy and biomarkers that can be used as mortality predictors. The main mechanism of pesticides toxicity is via inhibition of acetylcholinesterase enzyme responsible for the degradation of the neurotransmitter acetylcholine. This abrupt increase in acetylcholine levels leads to a cholinergic surge with continuous stimulation of receptors leading to the manifestation of signs and symptoms that vary according to the route of exposure to organophosphates ^(3,4). Another suggested mechanism was the oxidative stress induced by the pesticides ⁽²⁾.

However, only few studies focused on biomarkers and their quantitation. Results emphasized the importance of detecting the levels of serum cholinesterase as a prognostic indicator for acute toxicity ^(5,6). Nevertheless, it has been shown that the reliability on serum cholinesterase levels is controversial ^(2,7,8). Oxidative stress biomarkers (malondialdehyde (MDA) and total antioxidant capacity (TAC)), activity of the apoptotic biomarkers (caspase 3 and caspase 9) and pseudocholinesterase (p.ChE) were further investigated as mortality predictors ⁽²⁾. Significantly, there is paucity of evidence regarding the value of biomarkers addressing the involvement of nerve damage resulting from organophosphate poisoning in acute and chronic toxicities despite the accumulating evidence of their chronic neurological impact associated with their action on neurotoxic esterase ^(5,8)

AIM OF THE STUDY

To assess the possible prognostic value of markers of neuroinflammation and damage by a full proteomic and glycomic profile of acute and chronic organophosphate exposure patients. The profiling will be generated together with an assessment of their genotoxic effect. This will be conducted in parallel to the assessment of traditional markers of inflammation and oxidative stress.

PLAN OF THE STUDY

Study setting:

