- Acute exposure patients will be recruited from the Poison Center and Emergency Department of Alexandria Main University Hospital.
- Chronic exposure patients will be recruited from farm field workers with a confirmed history of repeated occupational exposure to organophosphate pesticides.
- Control subjects will be recruited from city dwellers without any medical conditions (healthy subjects) with comparable age and gender.

Study design:

Type of the trial: cross-sectional trial

Inclusion criteria:

Chronic Patients: Adult males with age above 18.

Acute Patients: Adult males and females with age above 18 .

Controls: Adult males and females with age above 18 without previous exposure to organophosphate pesticides.

No restrictions on comorbidities in the three groups except those mentioned under Exclusion Criteria.

Exclusion criteria:

Pediatric patients, patients with neurological diseases (Parkinsonism, epilepsy, Alzheimer's disease , etc.) and any patient who does not meet the inclusion criteria.

Target population:

Patients with acute and chronic exposure to organophosphates.

Sample size: Total number between 60 to 90 patients, divided into three groups:

- 1- Controls without previous exposure to organophosphates ($n \geq 15$).
- 2- Patients with chronic exposure to pesticides ($n \geq 30$).
Patients with acute exposure to organophosphates ($n \geq 30$).

Outcome assessment:

Identification of a neuroinflammatory biomarker that correlates with nerve injury.

Type of sample and method of selection:

Convenience sample through nonprobability sampling methods

Data collection methods and tools:

1-Patient demographics and data regarding chronic patients including: 1) history of organophosphates exposure 2) compliance to safety instructions during handling of pesticides 3) medical history 4) general health status 5) cholinergic symptoms if any will be recruited through a questionnaire answered by the patients on the day of recruitment.

2-Blood sample collection with required preparations for serum extraction.

3- Laboratory analysis for some biomarkers.

4-Proteomic and glycomic analysis to identify the biomarker that correlates with nerve injury⁽⁹⁾.

Ethical consideration:

1. The researcher will seek the approval of the Ethics Committee of Faculty of Pharmacy & Alexandria University for conducting the research.

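### The only listed outcome is a biomarker that correlates with nerve injury, but no data item is identified as the measure of nerve injury

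*Protocol*

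**What the plan says.** Outcome assessment in the protocol contains a single entry, "Identification of a neuroinflammatory biomarker that correlates with nerve injury". The last item under Data collection methods and tools repeats the target: "Proteomic and glycomic analysis to identify the biomarker that correlates with nerve injury".

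That section lists four items:

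1. Demographics and a questionnaire, introduced as "Patient demographics and data regarding chronic patients including" and followed by five topics: past exposure, adherence to safe handling, medical history, general health and, last, "cholinergic symptoms if any will be recruited through a questionnaire answered by the patients on the day of recruitment".
2. Blood drawn and prepared for serum.
3. "Laboratory analysis for some biomarkers", with no marker named.
4. The proteomic and glycomic profiling.

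Study design gives "Type of the trial: cross-sectional trial", and no later visit is listed. The Aim adds genotoxicity and conventional inflammatory and oxidative-stress markers, but these are not entered as outcomes. Neurological disease appears under Exclusion criteria, not as something graded in enrolled participants.

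**The concern.** The outcome is a relation between two things: a candidate marker and nerve injury. The protocol says where the candidates come from. It does not say what stands for nerve injury, how that is measured, or in whom.

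If the study is run as written, the team will hold a set of marker values, group labels and some questionnaire answers, with no agreed standard for declaring that any marker meets the outcome. The easiest result to obtain is a marker that differs between exposed and unexposed people. Without a reference, nothing stops such a marker from being reported as one of nerve injury. That is a different claim and one that the data would not have tested.

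**Working it through.** The protocol gives no figure to reproduce on this point, so the check is a comparison of its sections.

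**Step 1. Is any data item the nerve injury side of the correlation?**

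| Data item | Content | Identified as the nerve injury measure? | Groups covered |
|---|---|---|---|
| 1 | Demographics; questionnaire on five topics | No | Topics worded for chronic patients |
| 2 | Blood and serum | No; a specimen | No limit stated |
| 3 | Unnamed laboratory biomarkers | No | No limit stated |
| 4 | Proteomic and glycomic profile | No; source of the candidates | No limit stated |

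Count: 0 of 4. The title, Aim, eligibility criteria and Statistical analysis section supply no neurological examination, score, nerve conduction test or named reference marker either.

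**Step 2. Could cholinergic symptoms serve?** They are the closest clinical variable. Two things count against them. First, the sentence ties the questionnaire topics to chronic patients, and one topic, adherence to safe pesticide handling, makes little sense for unexposed controls. On that reading the count of named clinical variables with any neurological bearing is one at most in chronic patients, and none in acute patients or controls. Second, the Introduction explains such symptoms by accumulation of acetylcholine at its receptors, and separately links long-term neurological effects to action on a different esterase. The protocol's own account therefore does not equate the symptoms with nerve damage.

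**Step 3. What can the listed data show?**

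- Marker against exposure group: a difference associated with exposure, or with whatever else separates the groups. For controls the source is stated as "Control subjects will be recruited from city dwellers without any medical conditions (healthy subjects", while chronic patients are farm workers.
- Marker against exposure history or symptoms in chronic patients: a relation to dose history or to cholinergic effect.
- Marker against marker: an association between two serum quantities, neither designated as the standard.

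None of the three is, by itself, a correlation with nerve injury.

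**Step 4. Why naming a reference is not quite enough.** Let M be a marker, R a nerve injury reference and G the exposure group. Then

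Cov(M, R) = E[Cov(M, R | G)] + Cov(E[M | G], E[R | G]).

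If M and R are unrelated within every group, the first term is zero. If exposure shifts the mean of both, the second term is not, and the pooled data show a correlation produced by exposure alone. The relation must therefore be assessed within group or with adjustment for group.

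**The case against.** The strongest reply is that the protocol can be read as complete apart from one name. The title is "Assessment of the prognostic value of nerve damage biomarkers in acute and chronic organophosphate toxicity", and the Aim speaks of both neuroinflammation and damage. On that reading, neuroinflammatory candidates are set against a serum damage marker measured among the unnamed laboratory biomarkers, from serum already collected and with no limit to one group. Designating that assay before the data are seen could be done in an SAP or laboratory manual. The data list is also evidently a summary: the genotoxicity and oxidative-stress measurements promised in the Aim are not named there either.

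Much of this stands. It rules out three stronger readings that a reader might infer:

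- *That no nerve injury measurement will exist, or none outside the chronic group.* The documents do not support this. The laboratory item may include a damage marker in all three groups; what is missing is its designation. The chronic-only reading of the questionnaire is the natural one, but the sentence is loosely built.
- *That everything must be settled before recruitment or is lost.* This holds only for a measure asked of participants on the day. A serum marker needs designation before the data are seen, and acute patients' hospital charts, where they exist, could be abstracted later.
- *That the defect can be sized by a false-positive rate or a detectable correlation.* The protocol gives no number of candidate markers and describes no after-the-fact choice of reference. Any such figure would rest on assumed inputs, so none is part of this point.

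The reply does not remove the point. A possible marker that nobody has designated does not define the outcome. If a clinical reference is intended, an SAP cannot create a variable that was never collected. The outcome and its data source belong in the protocol, and here the outcome names a quantity that the data list does not identify.

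**Conclusion.** The point holds. The only listed outcome depends on a nerve injury measure that the protocol does not identify: 0 of 4 data items is so designated, and the nearest clinical item is probably confined to one of three groups and is explained by the protocol through a different mechanism. The 0 of 4 is a count of what the text designates, not an estimate of bias.

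The consequence is one of interpretation. The study could find a marker that differs by exposure, or that tracks symptoms or another marker, and would have no stated basis for calling it a correlate of nerve injury.

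The conclusion rests on two readings: that the questionnaire topics are for chronic patients, and that the laboratory item designates nothing. If the first is wrong, cholinergic symptoms would be available more widely but still would not be named as nerve injury. If an unseen document designates a serum damage marker in advance, the protocol needs only to say so and to keep that marker out of the candidate set.

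**What to change.** In Outcome assessment and in Data collection methods and tools, name one nerve injury reference that is excluded from the candidate markers and collected the same way in every group where the correlation will be tested. Two options fit the present design:

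- **One serum nerve damage marker, designated before the data are seen.** This is closest to the current protocol and costs the naming of one assay, plus running it if it is not already planned. Its weakness is that a serum reference is only a surrogate for nerve injury.
- **A short neurological symptom score added to the day-of-recruitment questionnaire, for all groups.** This costs a few questions and has to be in place when participants are seen. Scores may vary little in controls and may partly reflect cholinergic effects in acute patients.

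Under either option, state that the correlation is assessed within exposure group or adjusted for group, so that exposure alone cannot produce it.

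If no reference can be collected, restate the outcome as a biomarker that differs between exposure groups and drop the claim of correlation with nerve injury. That costs nothing in data collection and leaves a more modest claim that the listed data can address.

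### One cross-sectional sample both selects a marker from a full profile and supplies its value; unless selection is corrected for, the chosen marker's correlation is biased upward, so the outcome should be candidate nomination

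*Protocol*

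**What the plan says.** Under Outcome assessment the protocol gives a single outcome: "Identification of a neuroinflammatory biomarker that correlates with nerve injury". No marker is named there and no threshold is set.

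Item 4 of Data collection methods and tools says where the marker comes from: "Proteomic and glycomic analysis to identify the biomarker that correlates with nerve injury". The Aim of the Study describes the search space as a full profile and gives the purpose as "To assess the possible prognostic value of markers of neuroinflammation and damage". The title also speaks of prognostic value.

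All of this happens in one cross-sectional convenience sample: "Total number between 60 to 90 patients, divided into three groups". The minimums are 15 controls, 30 chronically exposed and 30 acutely exposed. No hold-out part and no second cohort is described. The Statistical analysis section promises only suitable techniques. It states no significance level, selection rule or estimator.

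**The concern.** Picking a marker because it correlates best, and then reporting that correlation from the same people, gives an estimate that is too large on average. The size of the excess depends on how many candidates were searched and how few people were studied. A full profile searched in under 100 people is the setting where it matters.

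There are two separate problems. One is false declaration: if every candidate were tested at an unadjusted level, some marker would probably correlate even if none is related to nerve injury. Multiplicity control deals with that. The other is selection bias in the reported estimate, and multiplicity control does not deal with it. A stricter threshold means that only unusually large observed correlations are reported.

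The outcome wording and the single-sample design are fixed in the protocol. An SAP can correct the estimate, but it cannot supply an independent sample. A one-stage search in one sample can nominate candidates. The present wording lets it be reported as having identified a marker and assessed its value.

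**Working it through.** **Inputs from the protocol.** Group minimums: 15 + 30 + 30 = 75. A total of 60 to 74 cannot meet them, so the working range is 75 to 90. No alpha, power, effect size or candidate count is given, so the sample size itself cannot be reproduced.

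**Assumptions.** Number of eligible candidates m from 10 to 1000. Two-sided 0.05 per candidate where a test is needed. Markers independent unless stated.

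**1. Chance of at least one apparent hit, no true marker, unadjusted tests.** Formula: 1 − 0.95^m.
- m = 10: 40%
- m = 20: 64%
- m = 100: 99.4%

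Correlation between markers lowers this. For m = 100 in blocks of 20 at n = 75, simulation gives roughly 95%, 72% and 60% for within-block correlations of 0.5, 0.8 and 0.9. In smaller blocks of 10 with m = 300 it stays at 99% to 100%.

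**2. Largest |r| by chance alone.** Each null r is simulated as t/√(n − 2 + t²), with t on n − 2 degrees of freedom. The largest of m is taken and averaged over runs.

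| n | m = 20 | m = 100 | m = 1000 | nominal 5% cut-off |
|---|---|---|---|---|
| 75 | 0.25 | 0.31 | 0.39 | 0.23 |
| 90 | 0.23 | 0.29 | 0.36 | 0.21 |

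With 10 candidates at n = 75 the mean is 0.22.

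**3. If one real marker exists.** One true marker with r = 0.3 among 300 independent candidates:
- n = 75: the top marker shows mean |r| 0.37. The true marker is the one picked 34% of the time. The average true r of the picked marker is 0.3 × 0.34 ≈ 0.10.
- n = 90: 0.35, 42%, and 0.3 × 0.42 ≈ 0.13.

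**4. Why error-rate control does not cure the estimate.** With family-wise control over 300 candidates (0.05/300 each), the chance of any false marker is about 4.9%. The cut-off in |r| rises to 0.42 at n = 75 and 0.39 at n = 90. A marker whose true r is 0.3 can then be declared only when its observed |r| exceeds 0.42 at n = 75. Every such reported value is at least 0.12 too high (0.42 − 0.30). Power for that marker is 13% at n = 75 and 19% at n = 90.

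**5. What independent confirmation of one marker would need.** Fisher z, 80% power, two-sided 0.05: n = ((1.96 + 0.84)/atanh r)² + 3. This gives 85, 47 and 30 people for true r = 0.3, 0.4 and 0.5. A hold-out of 30 taken from the present sample would have 36%, 60% and 81% power.

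**The case against.** The strongest objection is that this belongs to an SAP that is not at hand. The protocol does not say that markers will be tested unadjusted. With family-wise or false-discovery control, the chance of any declared marker under a complete null falls to about 5%. Resampling that repeats the selection is ordinary SAP content and needs no second cohort. This stands as a limit on the claim. A reader might infer that the reported correlation will be inflated, or that the outcome is bound to be met by chance. The documents do not support either without the condition that selection goes uncorrected. What remains is that the outcome promises identification from a single-stage search, and that wording is the protocol's own.

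The candidate pool is also uncertain. The outcome concerns neuroinflammatory markers, so not every protein or glycan need be eligible. With 10 or 20 eligible markers the figures are smaller (40% and 64%; mean largest |r| 0.22 and 0.25 at n = 75). They are still material.

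A reader might also compute the chance-level AUC for acute patients against controls. That measures group discrimination, not correlation with nerve injury, and the protocol names no AUC, so it does not bear on this outcome. Analysis within 60 exposed people or one group of 30 would give larger chance correlations, but the protocol does not say that the analysis is so restricted.

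Finally, the aim speaks only of possible prognostic value, and no clinical-use claim is made. That hedge is real, but it does not extend to the outcome or to data collection item 4.

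**Conclusion.** The point holds in conditional form. The protocol fixes an open identification outcome, a full profile as the search space and one sample with no confirmation set. Unless selection is corrected for, the best marker's correlation is biased upward, and error-rate control alone leaves that bias in place. With no true marker, a top |r| of about 0.25 to 0.39 at n = 75, or 0.23 to 0.36 at n = 90, is what chance produces on average for 20 to 1000 independent candidates. The 64% and 99.4% chances of an apparent hit apply only to unadjusted 0.05 tests of 20 and 100 independent candidates, and strong correlation between markers lowers them. The candidate count, test level and correlation structure are assumptions. That selection biases the estimate upward does not depend on their exact values; how large the bias is does. The change is worth making because it is cheap and sets what the study can conclude.

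**What to change.** Reword the outcome to: *Nomination of candidate neuroinflammatory or nerve-damage biomarkers for confirmation in an independent sample.* Bring the title, the aim and data collection item 4 into line with it, so that the protocol does not promise nomination in one place and identification or prognostic value in another.

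State in the protocol that any correlation for a marker selected from the profile is reported from cross-validation with the selection repeated inside each fold, together with a max-statistic permutation p-value. If a short list of nerve-damage markers is fixed before assay results are seen, call it a prespecified priority list of candidates. Calling it a confirmatory family would contradict an outcome that only nominates.

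Splitting the present sample is possible but weak, as the hold-out power above shows.

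Cost: wording changes and some extra computing, with no additional patients or assays. The claim becomes more modest and the reported correlations will be smaller.
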